Health care claims data were provided at the individual employee level by Cigna and were used to calculate spending and utilization variables. These administrative data are available for all worksites (treatment, primary control, and secondary controls), but only for the roughly 37% of employees who were enrolled in a BJ's employer-sponsored Cigna health insurance plan at any given time. Full time workers were more likely to have Cigna coverage than part-time workers. We analyzed medical claims for BJ's employees (but not their dependents, who were not directly exposed to the treatment).

We aggregated medical spending and utilization at the employee level across our 36-month treatment period. To standardize utilization outcome variables across employees who may have been employed and in our sample for different lengths of time, we normalized outcomes for partial-year enrollees to annual values. For each employee, we exclude any claims with service dates prior to either the employee's hire date or the start of Cigna eligibility status as well as any claims with service dates more than 30 days after the employee's termination or end of Cigna enrollment.

We examined the following outcomes at the individual level as well as the worksite level. In worksite-level analyses, results are shown per 2000 work hours for all the continuous outcomes to normalize across sites of different sizes. An exception was the number of distinct medications, which we constructed at the worksite level using a weighted average of individual values based on hours worked at the worksite.

- **Total medical spending:** We defined total medical spending per year as the sum of all payments made for health care – deductibles, copayments, coinsurance, insurance payments, and “amount paid by other carrier” – that appear on an employee's claims.
- **Medical utilization:** We defined three medical utilization variables (i.e. counts of services provided):
 - *Office Visits:* We defined an office visit as a claim line with site of care as “office” or “on-campus outpatient hospitals” and service type as “physician visit.” We counted as one office visit such an occurrence at the level of a unique combination of patient, service date, and provider specialty. In other words, if an office code appears on multiple claim lines on the same date and billed by the same provider specialty, we counted these as a single visit. We do not include office visits that occurred with the site of care as

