“inpatient hospital.” Similarly, we defined an urgent care visit as a claim line with a site of care as “urgent care facility” and identified preventive care visits by using preventive visit CPT codes in claims.

- *Hospitalizations*: We defined a unique hospitalization as a set of contiguous days on which a patient has a claim line with site of care “inpatient hospital.”
- *Emergency Room visits*: ER visits are identified from claim lines with site of care “Emergency Room – Hospital” and service type “emergency facility” or “emergency medical care.” We include the service type restriction so that we avoid double counting an ER visit when a claim for imaging, labs, or prescription drug is received a day or two later than the actual ER visit. Similar to hospitalizations above, we treat claims for the same or continuous days as a single emergency room visit.
- **Total prescription drug spending**: We defined total prescription drug spending as the sum of all payments, inclusive of cost-sharing, that appear on an employee’s claims at the annual level, scaled using the method described above.
- **Prescription drug utilization**: We defined two pharmaceutical utilization variables:
 - *Number of Distinct Medications*: We defined number of distinct medications as the total count of each unique prescription drug molecule. Unlike the other medical and pharmaceutical outcomes, this outcome is not annualized.
 - *Number of Medication Months*: We used the total quantity and duration of medication supplied to obtain the number of medication months. Because a person can be taking multiple medications at the same time, the number of medication months can be greater than the number of months a person is enrolled.

Table 4 provides summary statistics for medical and pharmaceutical spending and utilization among the control worksites during the treatment period. While substantial additional granularity is available in the claims data, our sample sizes do not in general support condition-specific analyses.

B. Primary Data

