Notes: Table reports the coefficient on TREATMENT from estimating equation (1) by OLS (column 2), and the coefficient on PARTICIPATION from estimating equation (2) by IV (column 3). Standard errors are listed in parentheses. Column 1 reports the mean of each employment outcome in the control group for each sample (with standard deviation in parentheses, followed by the number of observations for each outcome). All regressions will include demographic and employment controls (age, sex, age-sex interactions, race/ethnicity, Cigna coverage status, full-time status, paid hourly status, and job category) and cluster standard errors at the worksite (for employee-level regressions). Employee-level and stably employed subsample control means are weighted by a weight that balances treatment and control on demographic characteristics. Worksite-level control means are not traditionally weighted: individual-level records are collapsed at the worksite-level and weighted by the total number of hours worked at each worksite. For worksite level results on tenure, the outcome was defined as the percent of total days at the worksite during the study period that was worked by employees at the worksite.

§ Tenure was defined as the number of days worked during the treatment period for the employee-level mean and stably employed subsample mean; it was defined as the percent of the entire treatment period worked by employees in the worksite-level mean.

Table 4: Impact on Medical & Pharmaceutical Spending and Utilization

	Employee-level			Stably Employed Subsample			Worksite-level (per 2000 work hours)		
	Mean in Control Group (1)	Reduced Form (Linear) (2)	2SLS (Linear) (3)	Mean in Control Group (1)	Reduced Form (Linear) (2)	2SLS (Linear) (3)	Mean in Control Group (1)	Reduced Form (Linear) (2)	2SLS (Linear) (3)
Medical Spending									
Total Spending	4800.57 (18559.82)			4721.85 (19056.92)			5044.74 (2994.54)		
Medical Utilization									
Number of Office visits	3.90 (4.47)			3.95 (4.33)			4.21 (0.93)		
Number of Hospitalizations	0.09 (0.40)			0.08 (0.36)			0.08 (0.05)		
Number of ER Visits	0.28 (0.75)			0.26 (0.61)			0.27 (0.11)		
Pharmaceutical Spending									
Total Spending	1237.60 (6921.32)			1227.32 (7115.67)			1317.72 (1145.17)		
Pharmaceutical Utilization									
Number of Distinct Medications	5.49 (6.44)			5.91 (6.54)			6.00 (1.30)		
Total Medication Months	11.20 (19.31)			11.41 (19.37)			12.39 (4.38)		
N	7,174			5,779			135		

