Notes: Employees are included if they answered at least 1 question on the PHA. Demographic characteristics are plausibly unaffected by the treatment. Demographics are taken from the Team Member database supplied by BJ's and based on the first entry for an individual during the treatment period. Age is defined as of December, 2014 (pre-treatment). Column 1 reports the means for employees in the treatment group while column 2 reports the means for the primary control employees. Treatment status is defined by the first worksite an employee appears in during the treatment period. Column 3 reports the p-value for the comparison between the employees at treatment worksites and the employees at primary control worksites. All regressions are weighted by a weight that balances treatment and control on demographic characteristics and cluster standard errors by worksite.

Panel C: Cigna Insured Subsample

	(1) Treatment (n=1385)	(2) Primary Control (n=1354)	(3) Primary + Secondary Control (n=7174)	(4) (1) vs (2) P value	(5) (1) vs (3) P value
Demographics					
Age (yrs)	42.7	42.1	42.6	0.321	0.836
Female (%)	44.4	43.8	44.6	0.768	0.949
Race (%)				0.996	>0.999
Black	16.9	14.9	17.7		
White	62.7	66.6	61.2		
Hispanic	14.7	14.9	15.9		
Other	5.6	3.7	5.2		

Notes: Employees are included if they had at least 1 month of Cigna health insurance coverage. Demographic characteristics are plausibly unaffected by the treatment. Demographics are taken from the Team Member database supplied by BJ's and based on the first entry for an individual during the treatment period. Age is defined as of December, 2014 (pre-treatment). Column 1 reports the means for employees in the treatment group while columns 2 and 3 report the means for the primary control employees and all control employees (primary and secondary), respectively. Treatment status is defined by the first worksite an employee appears in during the treatment period. Column 4 reports the p-value for the comparison between the employees at treatment worksites and the employees at primary control worksites and column 5 reports the p-value for the comparison between the employees at treatment worksites and all employees at control worksites. All regressions are weighted by a weight that balances treatment and control on demographic characteristics and cluster standard errors by worksite.

Panel D: Stably Employed Subsample

	(1)	(2)	(3)	(4)	(5)

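### The hospitalization count has no gap allowance, so a line-free day or an inpatient line dated two or more days late can turn one stay into two; how often this happens cannot be found from the documents

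*Combined protocol and SAP*

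**What the plan says.** Section IV.A2 (Medical and pharmaceutical claims data, Medical utilization) rebuilds hospital stays from claim lines: "We defined a unique hospitalization as a set of contiguous days on which a patient has a claim line with site of care" inpatient hospital. It gives no permitted gap, no admission or discharge date, no facility-claim identifier and no service-type condition. It also does not say whether a line is placed on one service date or on every day of a from-through span.

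The ER bullet that follows uses the same merging logic: "we treat claims for the same or continuous days as a single emergency room visit", described there as similar to the hospitalization rule. It adds a protection that the hospitalization rule lacks: "We include the service type restriction so that we avoid double counting an ER visit when a claim for imaging, labs, or prescription drug" arrives a day or two after the visit. Office visits also carry a service-type condition.

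The count is then annualized ("we normalized outcomes for partial-year enrollees to annual values"). It is reported in the Table 4 row "Number of Hospitalizations", with control means (SD) of 0.09 (0.40) for employees, 0.08 (0.36) for the stably employed and 0.08 (0.05) at worksite level.

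**The concern.** The plan recognizes that ancillary lines in this claims feed can be dated after the encounter they belong to. It acts on that for ER visits and leaves the hospitalization rule open. Followed literally, one stay can produce several hospitalizations, and how many depends on which days happen to carry a line.

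This affects what the outcome measures. A stay of one or two days has no interior day and cannot be split by a line-free day, whereas a long stay can be split repeatedly. The count may therefore carry some length of stay and billing density along with admissions. It may also sit above the true rate and be noisier than it need be, for an outcome that is already rare.

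**Working it through.** **Inputs from the documents.** The counting rule (IV.A2); employee-level control mean 0.09, SD 0.40 (Table 4); Cigna samples of 1,385 treatment and 7,174 control employees (Table 8, Panel C). The control mean cannot be reproduced without claim-level data, and the plan gives no power calculation for this outcome.

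**Step 1: apply the rule to a five-day stay (days 1 to 5).** The count is the number of unbroken runs of days with a line.

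| Days with an inpatient line | Rule as written | One line-free day bridged |
|---|---|---|
| 1,2,3,4,5 | 1 | 1 |
| 1,2,4,5 | 2 | 1 |
| 1,3,5 | 3 | 1 |
| 1–5 and 6 (next-day line) | 1 | 1 |
| 1–5 and 7 (line two days late) | 2 | 1 |
| 1 and 5 only | 2 | 2 |
| Discharge day 3, readmission day 4, lines 1–6 | 1 | 1 |

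A line-free interior day splits the stay only if lines carry single dates. The late line splits it under either date structure. The last row shows that the rule can also undercount.

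**Step 2: possible size (assumptions, not document figures).** Let q be the share of interior days without a line and s the share of stays with an inpatient-coded line two days late. For a stay of fixed length L ≥ 3 with first and last days billed and independent gaps, the expected count is 1 + q + (L − 3)q(1 − q) + s.

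- L = 3, q = 0.05, s = 0: 1 + 0.05 = 1.05.
- L = 6, q = 0.05, s = 0: 1 + 0.05 + 3 × 0.0475 = 1.19.

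Simulation with varying stay lengths (40,000 stays per scenario, s = 0) gives similar counts per true stay:

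| Mean stay (days) | q = 0 | q = 0.02 | q = 0.05 | q = 0.10 |
|---|---|---|---|---|
| 3 | 1.00 | 1.025 | 1.063 | 1.125 |
| 4.5 | 1.00 | 1.053 | 1.130 | 1.247 |
| 6 | 1.00 | 1.081 | 1.203 | 1.385 |

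Late lines add about s, so late lines alone in 5 to 10% of stays give 1.05 to 1.10. The middle case (4.5 days, q = s = 0.05) gives 1.18. The most adverse corner (6 days, q = s = 0.10) gives 1.48.

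**Step 3: effect on the control mean.** True rate = 0.09 / (1 + overcount).

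- 0%: 0.090
- 5%: 0.09/1.05 = 0.086
- 10%: 0.09/1.10 = 0.082
- 20%: 0.09/1.20 = 0.075

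Table 4 is rounded. In the middle case, 0.085 to 0.095 divided by 1.18 gives 0.072 to 0.081.

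**Step 4: effect on variance.** In the middle case the relative variance of the event count rises by 12 to 14%, depending on the spread of stay lengths. That is at most about 7% on the standard error (√1.14 = 1.07). It is an upper bound, because variation between people in admission rates is not multiplied.

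**Step 5: could a length-of-stay effect show up as an admission effect?** Suppose controls average 6 days, treated employees average 3, and true admissions are equal.

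- q = 0.05: true rate 0.09/1.203 = 0.0748; treated count 0.0748 × 1.063 = 0.0795; difference 0.010 per year.
- q = 0.10: true rate 0.09/1.385 = 0.0650; treated count 0.0650 × 1.125 = 0.0731; difference 0.017 per year.

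For comparison, the unclustered standard error is 0.40 × √(1/1385 + 1/7174) = 0.0117. The detectable difference (two-sided 0.05, 80% power, both assumed) is 2.80 × 0.0117 = 0.033 per year, about 37% of 0.09. Clustering would normally enlarge it.

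**The case against.** The strongest reply is that no error in the count has been demonstrated. If facility lines carry from-through dates covering the stay, interior splitting disappears, and the documents do not say which structure applies. This stands, and it is why the range starts at nil.

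The ER comparison is also looser than it looks. An ER visit is short, so ancillary lines easily fall outside it; during a multi-day stay most fall inside the run. A late line adds a count only if it is coded inpatient hospital and at least one line-free day precedes it. The plan's own worry is "a claim for imaging, labs, or prescription drug is received a day or two later than the actual ER visit", and a line one day later is absorbed. This stands too, and the assumed 5 to 10% late-line rate has no support in the documents.

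A reader might infer that the missing service-type condition is the defect and that copying the ER restriction would cure it. The documents do not support that. Because any service type qualifies, more days carry a line; a restriction by itself removes lines and can create more gaps.

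Finally, the same rule applies in both arms. A common inflation factor creates no spurious effect when the program does nothing, and total medical spending in Table 4 does not depend on this count. Both points stand. They limit the consequence but do not settle what the rule counts, since the date field is unstated and no gap is allowed.

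**Conclusion.** The point holds as a weakness in the definition. The written rule can count one stay more than once by two identifiable routes, one of which the plan itself recognizes for ER visits. Its size is unknown: nil if facility lines span the stay and no late lines occur, and about 5 to 20% under moderate assumed billing rates, with higher values only in adverse corners of the assumptions. The expected consequence is an inflated level, some added variance and, if lines carry single dates, some dependence on length of stay.

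Two stronger readings are tempting. One is that the control rate of 0.09 is overstated; the documents give neither the date structure nor the billing rates needed to show it. The other is that a program effect on length of stay would be reported as an effect on admissions. Even halving the mean stay from 6 to 3 days shifts the count by only about 0.01 to 0.02 per year under the assumptions above, below the roughly 0.033 detectable without clustering. Nothing in the documents suggests that splitting differs by arm.

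This is a cheap improvement worth making; it does not threaten the main conclusions.

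**What to change.** State which date field places a claim line on a day. Where the claims carry facility admission and discharge (from-through) dates, build each hospitalization from them. Otherwise, merge inpatient-hospital lines separated by a small pre-specified gap, for example one or two line-free days, into one hospitalization. Facility dates are preferable: a five-day stay with lines only on its first and last days has three line-free days and would still split. Do not add a service-type restriction without gap bridging.

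Regenerate the control-group hospitalization row of Table 4 under the new rule before the arms are compared. The plan's opening section says that post-treatment outcomes over the three-year window have not yet been compared, so the change can still be made without raising a specification-search question.

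The cost is a sentence or two in the plan and a small programming change on claims already held. The downside is that a true readmission within the bridged gap is merged with the first stay; the present rule already does this for next-day readmissions. The documents do not say whether phase 1 used the same definition. If it did, keeping the contiguous-day count as a sensitivity row would preserve comparability.

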Among these worksites, we randomly selected 25 “treatment” worksites that would receive the wellness program and 25 “primary control” worksites for phase 2.⁵ These primary control worksites participated in data collection through PHAs and in-person biometric screenings, but did not receive the wellness program treatment. **Figure 1** shows the locations of the 25 treatment and 25 control worksites across the Eastern U.S. The remaining 110 worksites served as “secondary controls.” which were included in analyses of administrative data. Thus, the primary data described below was collected from the 50 treatment and primary control worksites; administrative data were compiled for all 160 worksites. **Figure 2** shows a Consolidated Standards of Reporting Trials (CONSORT) flow diagram for our phase 2 evaluation, including the sample sizes of treatment and control groups.

⁵ For the first 18 months of the study (phase 1), there were 20 treatment and 20 primary control sites.

Randomization at the worksite level allows us to assess the effects of interventions that aim to affect workplace culture or operate on a group level, such as using common break rooms to stage nutrition demonstrations, team-based activities, or worksite level prizes.

IV. Data

Our analysis focuses on outcomes from five data categories. The Table below displays the source of each data set and the study population from which it is derived.

Summary of the Components of Data Collected				
Data	Source	Treatment Worksites (25)	Primary Control Worksites (25)	Secondary Control Worksites (110)
Administrative Data				
Employment records	BJ's	All employees	All employees	All employees
Claims data (medical and pharmaceutical)	Cigna (via BJ's)	Employees insured by Cigna	Employees insured by Cigna	Employees insured by Cigna
Primary Data				
Biometric screening data	Wellness Workdays	Employees completing screening	Employees completing screening	None (by design)
Personal Health Assessment	Wellness Workdays	Employees completing survey	Employees completing survey	None (by design)
Participation in the treatment	Wellness Workdays	All employees	None (by design)	None (by design)

A. Administrative Data

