Primary data consist of biometric data collected during in-person screenings conducted by registered nurses and self-reported data gathered from PHA surveys. The biometric data includes blood pressure, height and weight (inputs into the calculation of BMI), and blood measurements of cholesterol and blood sugar. PHAs contain self-reported information on health behaviors. Unlike the administrative data, these primary data are available for individuals in the 25 treatment worksites and the 25 primary control worksites who completed the PHA and biometric data collection between 08/01/2017 and 10/31/2017.

B1. Biometric screening data

In the treatment and primary control worksites, we conducted biometric screenings after the conclusion of the last wellness module. The screenings were conducted by registered nurses in the worksites, who met with employees individually. We defined all of the following biometric outcomes as continuous variables.

- Total cholesterol
- High-density lipoprotein (HDL) cholesterol
- Blood glucose (mg/dl)
- Systolic blood pressure
- Body mass index (BMI): weight in kilograms divided by the square of height in meters

Table 5 provides summary statistics for biometric screening data from employees who were screened in the control worksites.

B2. Personal Health Assessment Data

At the conclusion of the wellness modules, we also fielded PHA surveys in each of the treatment and primary control worksites. Employees were asked to complete a paper survey with questions relating to their health behaviors, mental health, and general wellbeing. We use this dataset to assess the impact of the wellness program on employees' self-reported health behaviors and perceived health status.

Based on an examination of the distribution of PHA responses collected from the control group, we examine the following outcome variables.

- **Health behaviors:**

Screenings and Exams

- *Percent of recommended tests received:* We pooled commonly recommended tests (based on age and sex) covered in the PHA and determined the share of those tests that respondents reported obtaining. These tests are cholesterol level, fasting blood glucose level, blood pressure, dental exam, colon cancer screening, mammogram, and pap smear.

Physical activity

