We designed our analyses based on two study samples. Our main study sample comprised all employees who worked for any duration of time at BJ’s Wholesale Club during the study period. In other words, we included any worker who worked at BJ’s for any length of time during the study period. This is the most inclusive sample.

A potential drawback of these sample inclusion criteria is the possibility of endogenous entry or exit based on the treatment itself. For example, a worker’s decision to join or leave employment at BJ’s Wholesale Club could be a function of the availability of, or exposure to, the wellness program. Therefore, we also defined a relatively stable subsample of employees who were continuously employed at BJ’s in the months before the treatment. This “stably employed” subsample comprised all employees working at BJ’s during, at minimum, the 13 consecutive weeks immediately prior to the onset of the treatment—and thus cannot have entered because of the treatment. Exit from this sample might still be endogenous in theory, however. We will therefore gauge the potential bias introduced by any observed differences in exit between treatment and control sites using a bounding exercise. Additional details on the construction of this subsample are provided below and in the appendix.

B. Balance between treatment and control

We tested balance between treatment and control groups on observable baseline characteristics. We examined balance on demographic variables (age, sex, and race) for all of the analytical samples. We also examined balance on job and employment characteristics in the pre-intervention period for the stably employed subsample, as they by construction were in jobs with characteristics defined prior to the intervention and thus exogenous to the treatment status.

As **Table 8** demonstrates at the employee level, our randomly assigned worksites were balanced on many employee characteristics, but not all. Notably, while treatment and control site workers

⁸ This indicator was our primary definition of participation in our prior phase 1 analysis. Given that we expanded the sample size for phase 2 (with a different total number of modules available), we believe the continuous measure is preferable here.

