Screenings and Exams						
Percent of recommended tests received	58.00 (32.51) 1,454			64.03 (30.80) 747		
Physical Activity						
Regular exercise (%)	53.79 (49.87) 1,440			54.56 (49.83) 737		
Number of hours sitting per day	3.73 (1.78) 1,444			3.71 (1.77) 741		
Nutrition						
Number of non-zero calorie drinks per day	1.36 (1.71) 1,443			1.21 (1.60) 742		
Read the Nutrition Facts panel (%)	58.91 (49.22) 1,443			61.66 (48.65) 739		
Consume at least 2 cups of fruit and 2.5 cups of vegetables per day (%)	54.13 (49.85) 1,441			57.60 (49.45) 738		
Weight Management						
Actively managing weight (%)	61.52 (48.67) 1,417			61.40 (48.72) 726		

Tobacco Use		
Smoker (%)	14.67 (35.40) 1,444	13.00 (33.65) 741
Domain 2: Health and Well-Being		
SF-8 score – physical summary score	51.56 (6.78) 1,427	51.65 (6.76) 735
SF-8 score – mental summary score	51.87 (8.47) 1,427	52.26 (8.07) 735
Unmanaged stress (%)	30.68 (46.13) 1,441	31.77 (46.59) 738
Unmanaged depression (%)	30.58 (46.09) 1,444	29.42 (45.60) 740
Stress at work (%)	39.69 (48.94) 1,447	44.35 (49.71) 743

Notes: Table reports the coefficient on TREATMENT from estimating equation (1) by OLS (column 2), and the coefficient on PARTICIPATION from estimating equation (2) by IV (column 3). Standard errors are listed in parentheses. Column 1 reports the mean of each self-reported health outcome in the control group for each sample (with standard deviation in parentheses, followed by the number of observations for each outcome). All regressions include demographic and employment controls (age, sex, age-sex interactions, race/ethnicity, Cigna coverage status, full-time status, paid hourly status, and job category) and cluster standard errors at the worksite (for employee-level regressions). Control means are weighted by a weight that balances treatment and control on demographic characteristics.

Table 7: Participation Rates

Panel A. Average Participation Rates by Module

	Phase 1								Phase 2			
Module	Take Charge of Your Health	Nutrition for a Lifetime	Club Cardio Challenge Round 1	Club Cardio Challenge Round 2	Maintain Don't Gain	Power Down the Pressure	Weight Loss Boot Camp	Movin' in May	Healthy and Fit	Nutrition for a Lifetime Round 1	Nutrition for a Lifetime Round 2	Step Challenge
Participation rate (%)	12.4	25.7	37.8	28.6	31.6	33.4	28.7	28.5	26.3	32.6	27.2	29.7

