Hispanic	14.2	17.4	17.7		
Other	7.0	5.8	6.9		

Panel A.2: All Employees – Weighted

	(1)	(2)	(3)	(4)	(5)
	Treatment (n=7288)	Primary Control (n=7377)	Primary + Secondary Control (n=41376)	(1) vs (2) P value	(1) vs (3) P value
Demographics					
Age (yrs)	33.0	32.9	33.1	0.867	0.934
Female (%)	45.9	46.9	45.8	0.614	0.964
Race (%)				0.999	>0.999
Black	25.8	24.4	25.9		
White	50.0	52.9	50.1		
Hispanic	17.3	16.9	17.2		
Other	7.0	5.8	6.8		

Notes: Demographic characteristics are plausibly unaffected by the treatment. Data are from the Team Member database supplied by BJ's and based on the first entry for an individual during the treatment period. Age is defined as of December, 2014 (pre-treatment). Column 1 reports the means for employees in the treatment group while columns 2 and 3 report the means for the primary control employees and all control employees (primary and secondary), respectively. Treatment status is defined by the first worksite an employee appears in during the treatment period. Column 4 reports the p-value for the comparison between the employees at treatment worksites and the employees at primary control worksites and column 5 reports the p-value for the comparison between the employees at treatment worksites and all employees at control worksites. In Table A.1, regressions are unweighted and standard errors are clustered by worksite. In Table A.2, all regressions are weighted by a weight that balances treatment and control on demographic characteristics and standard errors are clustered by worksite.

Panel B: Personal Health Assessment (PHA) Subsample

	(1) Treatment (n=1339)	(2) Primary Control (n=1336)	(3) (1) vs (2) P value
Demographics			
Age (yrs)	36.8	37.9	0.251
Female (%)	56.0	57.3	0.621
Race (%)			0.999
Black	21.4	18.6	
White	55.4	57.5	
Hispanic	16.7	18.2	
Other	6.5	5.7	

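### The PHA control group analysed (up to 1,454) is neither defined nor shown to be balanced; 1,339 treated against 1,336 primary controls should be the main comparison, and the sample behind the 0.001 SD weight tolerance should be named

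*Combined protocol and SAP*

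**What the plan says.** On where the data come from, Section IV.B states that "these primary data are available for individuals in the 25 treatment worksites and the 25 primary control worksites". The summary table in Section IV shows no primary data from the 110 secondary control worksites, by design.

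On balance, Section V.B says: "We examined balance on demographic variables (age, sex, and race) for all of the analytical samples". Table 8 Panel B gives 1,339 treated and 1,336 employees in a column labelled primary control. Its note reads: "Employees are included if they answered at least 1 question on the PHA".

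On the samples analysed, the control entry for recommended tests in Table 6 is "58.00 (32.51) 1,454" for all employees and "64.03 (30.80) 747" for the stably employed. Table 10 Panel A has 2,793 PHA completers, 1,454 of them controls. Panel B has 1,396, of whom 747 are controls. Panel C lists 110 surveyed worksites, 85 of them control.

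On assignment, Sections IV.A1 and VI.A place each employee in the arm of the first worksite, and Section IV.A1 gives as its reason that later moves may be endogenous. Section VI.E aggregates worksite data to that first site. Section VI.B mentions control-to-treatment movers, but only to explain why control participation is not exactly zero.

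On weights, Section V.B sets a tolerance of 0.001 SD on age, sex and race (0.01 SD in sensitivity analyses), calibrates to the overall study population, and reports every demographic as balanced after weighting. It does not say whether the weights are refitted in each subsample.

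**The concern.** One answered question is enough to be counted in Table 8 Panel B. Item non-response can therefore only bring an outcome below 1,336 primary controls, never above. Every all-employee control count in Table 6 is above it, so the analysed control group contains people outside the group that the text describes and Panel B displays.

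The likely source matters. Someone who started at a secondary control site was not surveyed there and could be surveyed only after moving to one of the 50 surveyed sites. No matching route adds people to the treatment arm, because all treatment sites were surveyed. That would be selection on a post-randomisation event, in one arm only, and on the kind of event that the plan itself treats as possibly endogenous.

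The plan also leaves two PHA control groups to choose between, although it exists to fix such choices before arms are compared. The weighting statement raises a related question: whether the balance it reports applies to the samples that are analysed.

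**Working it through.** **1. Reproducing the plan's totals (Table 10 total minus control, against Table 8 treatment).**

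| Sample | Table 10 | Table 8 treated | Table 10 control | Table 8 control |
|---|---|---|---|---|
| All | 48,664 − 41,376 = 7,288 | 7,288 | 41,376 | 41,376 (all controls) |
| Cigna | 8,559 − 7,174 = 1,385 | 1,385 | 7,174 | 7,174 (all controls) |
| Stably employed | 15,344 − 13,000 = 2,344 | 2,344 | 13,000 | 13,000 (all controls) |
| PHA | 2,793 − 1,454 = 1,339 | 1,339 | 1,454 | 1,336 (primary only) |

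The treated counts agree throughout. Only the PHA controls differ: 1,454 − 1,336 = 118, and 118/1,454 = 8.1%. The 13 control counts in Table 6 run from 1,417 to 1,454, which is 81 to 118 above 1,336.

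**2. Who the 118 may be.** In Table 10 Panel C, 110 − 85 = 25 treatment sites, and 85 − 25 = 60 control sites are not primary controls. Because worksite data are aggregated to the first site, these 60 read as sites of origin. Secondary-site starters number 41,376 − 7,377 = 33,999. If the 4.5% multi-site rate in Section IV.A1 applied to them (an assumption), about 1,530 would have moved, so 118 is a plausible number. Control completion of any module is 2.29% among PHA completers and 0.21% overall (Table 10 Panel A), which fits movers being concentrated among surveyed controls; some of these may have started at primary control sites.

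**3. Stably employed PHA sample.** Treated: 1,396 − 747 = 649, against 747 controls. Table 8 has no balance panel for this sample.

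**4. How different the 118 would have to be.** Take regular exercise (Table 6: control SD 49.87, n = 1,440), with 1,339 treated, equal SDs and no clustering, all assumed:

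- SE = 49.87 × √(1/1,339 + 1/1,440) = 1.89 points.
- The control mean shifts by 118/1,454 = 0.081 times the difference between extra and other controls.
- Difference that shifts the estimate by one SE: 1.89/0.0812 = 23.3 points, or 23.3/49.87 = 0.47 SD.

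**5. Weighted gaps in Table 8, treatment against all controls.** Standardised difference = |p1 − p2| / √{[p1(1 − p1) + p2(1 − p2)]/2}. Rounding to 0.1 point moves each difference by at most 0.1 point.

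- Full sample (Panel A.2): sex, Black, White and Hispanic are 0.002 to 0.003, all with a lower rounding bound of 0, so compatible with 0.001. Other race (7.0% v 6.8%) is 0.008, at least 0.004.
- Cigna (Panel C): Hispanic 14.7% v 15.9%, 1.2/36.0 = 0.033, at least 0.031. White 62.7% v 61.2%, 0.031.
- Stably employed (Panel D): Hispanic 16.2% v 17.7%, 1.5/37.5 = 0.040, at least 0.037. White 57.9% v 56.2%, 0.034.

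For 1,339 against 1,336 (Panel B, weighted), Black 21.4% v 18.6% gives 2.8/40.0 = 0.070.

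**The case against.** The best defence is that nothing conflicts. Section IV.B describes where data were collected, not how respondents are then assigned to an arm. Panel B counts primary controls, whereas Tables 6 and 10 count controls, so 1,336 can be a subset of 1,454. Secondary-site starters are also randomised controls, and analysing them as assigned is defensible. This largely stands as an account of how the counts arise. It does not supply a statement that the PHA sample includes such people, or a balance comparison that includes them. It also makes the case for restriction stronger, because under this account the extra controls are seen only after a move.

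A reader might infer more, and the documents do not support it:

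- That 60 undisclosed sites were surveyed. Aggregation to the first worksite makes 85 a count of origins.
- That other tables confirm the discrepancy. Biometric control counts (1,366 to 1,403) also exceed 1,336, but Panel B's rule concerns PHA answers, so it sets no ceiling for screening. The Table 11 column on considering weight loss sums to exactly 1,336, but nothing links that to Panel B. Neither is evidence.
- That the 0.001 SD tolerance is breached. That follows only if it was meant for each subsample. One set of full-sample weights reused in subsamples would give the pattern seen. The small gap in Other race is possible if that category was left unconstrained. All weighted demographic p-values in Table 8 are at least 0.193, so the balance statement may refer to tests. Not every subsample gap is large: sex in the Cigna sample differs by 0.004 SD.

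**Conclusion.** The point holds as a gap in sample definition with a likely, one-sided selection route. The 118 extra controls (8.1%), and the absence of any balance comparison for 1,339 v 1,454 or for 649 v 747, are established by arithmetic and by what Table 8 contains. That the 118 moved from secondary sites is an inference from the assignment rule and the 85 sites of origin.

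It would be too strong to say that the PHA results are materially biased. The size of any bias cannot be computed from the documents, and the threshold of about 23 points suggests it is probably small. Clustering would normally raise that threshold. The change is worth making because it is cheap and removes the problem, not because a large error has been shown.

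The weighting point is separate and smaller. The largest gaps, 0.033 SD (Cigna) and 0.040 SD (stably employed), are beyond rounding and above both stated tolerances, but they fall on covariates that are also in the regression. The fault is an unqualified statement that does not name its sample.

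**What to change.** - Make the main PHA analysis, including its first stage, the comparison of employees whose first worksite is one of the 25 treatment or 25 primary control sites (1,339 v 1,336). Keep the 1,454-control version as a sensitivity analysis.
- State who the 118 are and how they came to be surveyed. Show balance for every PHA sample used, including the stably employed one.
- Check whether screened controls include secondary-site starters and, if so, apply the same rule to biometrics.
- For the weights, either limit the 0.001 SD tolerance and the balance statement to the full sample against all controls and report achieved standardised differences for each subsample, or refit the weights within each analysis sample. Refitting is the more useful choice for the restricted PHA comparison, where the present weights leave 0.070 SD on Black.

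The cost is programming, about 8% fewer PHA controls, and somewhat more variable weights if they are refitted. The change does not address PHA non-response: 1,339/7,288 = 18.4% of treated and 1,336/7,377 = 18.1% of primary controls who ever worked in the period responded. Employees who moved from primary control to treatment sites stay in the arm to which they were assigned.
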